1. PROTOCOL SUMMARY AND/OR SCHEMA

- **Specific Objectives**

- To explore the feasibility of using Magnetic Resonance Imaging (MRI) alone in abdominal radiation therapy for treatment planning and target localization
- To demonstrate continuous positive airway pressure (CPAP) in motion reduction for abdominal radiation therapy

- **Eligibility**

- Patients who have liver or pancreas tumors and will be treated with radiation therapy
- Patients who are able to commit to Magnetic Resonance Imaging (MRI)

[figure not shown]
- **Required Sample Size**

- A maximum of 47 subjects (42 patients + 5 healthy volunteers) over a 24-month period

- **Study Design and Methods**

- All patients participating in the study will receive standard radiation therapy.
- Source of data for the study include CT, MRI, cone beam-CT (CBCT) and orthogonal kV/MV images and treatment plans.
- Patients will undergo both CT and MRI prior to abdominal radiation therapy and CBCT and orthogonal kV/MV images prior to each treatment delivery.
- A two arm study will be performed and patients will be enrolled into a given arm according to their eligibility. Arm 1 is for patients that are either not eligible for CPAP or that are unable to tolerate CPAP. These patients will undergo breath-hold and 4D imaging for both CT and MRI without CPAP. Arm 2 is for patients that are eligible for CPAP and able to tolerate CPAP. These patients will undergo breath-hold CT without CPAP, 4D-CT with and without CPAP and 4D-MRI with CPAP.
- Two specific aims will be investigated. In Aim 1, we will explore the feasibility of using a MRI-only in Radiation Oncology workflow. A probabilistic classification method will be utilized to generate a pseudo-CT from MRI to support treatment planning and image guidance for radiation therapy. The quality of the pseudo-CT will be evaluated by comparing it with CT. In addition, the reverse mapping will be investigated to create pseudo-MRI from CBCT to improve visualization of treatment targets and soft tissue prior to treatment delivery. In Aim 2, we will evaluate the utility of CPAP as a novel motion reduction methodology for patients with liver and pancreas cancer, to this end CT images with and without CPAP will be used. The evaluation will be based on the changes of motion magnitude, the achievable volumetric reduction in treatment target volumes, and doses to the targets and critical organs.

- **Schema**

Sample size: a maximum of 42 patients

2. INTRODUCTION AND BACKGROUND

2.1 Background

Radiation therapy is a technique that delivers high doses to tumors while minimizing doses to neighboring normal tissues in order to achieve optimal treatment outcome. Therefore, this technique requires high accuracy in target localization, one of major issues that are still being investigated in radiation therapy. Accurate targeting is particularly challenging when treating abdominal tumors, such as liver and pancreatic tumors, due to organ motion and the difficulty of distinguishing lesions from neighboring normal tissues using routine Computed Tomography (CT) images that are usually utilized for radiotherapy treatment planning.

In order to clearly identify lesions for radiation therapy, Magnetic Resonance Imaging (MRI) is often used due to its superior soft tissue visualization. MRI also has a potential for measuring biological functions and physiology using various functional imaging modalities, such as dynamic contrast-enhanced and diffusion-weighted images. These advantages allow MRI to be used for more accurate delineation of tumors and critical organs compared to CT and for treatment response assessment. However, MRI is not often used as a sole imaging modality in the radiation therapy workflow since the lack of electron density information precludes heterogeneity corrections, which are part of the standard of care in radiation therapy treatment planning. The use of multi-imaging modalities in the workflow requires an imaging registration step and therefore introduces uncertainties and errors (particularly in contouring) which are then propagated throughout the entire course of radiotherapy. To reduce these uncertainties, it has become of interest to streamline the workflow by implementing MRI alone in the planning process. Investigating the possibility of using MRI alone in the radiation therapy workflow is worthwhile for abdominal radiation therapy. The reason is that MRI is a necessary imaging modality to provide good tissue contrast for contouring abdominal tumors, and the registration uncertainty is likely larger in the abdomen than other body sites due to breathing and gastrointestinal motions.

In regard to organ motion, the largest motion of abdominal tumors and organs is caused by breathing, which complicates the planning process and affects the accuracy of radiation delivery. The American Association of Physics in Medicine (AAPM) Task Group 76 has recommended several methods to manage respiratory motion, and also recommended that respiratory management methods be considered if target motion is greater than 5 mm, or if normal tissue sparing is gained[1]. These methods include motion-encompassing methods, motion reduction methods and real-time tumor tracking methods. Motion-encompassing methods apply a motion margin to the targets to account for respiratory motion, resulting in excess normal tissue being irradiated. Current motion reduction methods use either breath-hold techniques or forced shallow breathing with abdominal compression. Real-time tumor tracking methods involve complicated techniques to detect the motion and dynamically reposition the radiation beam to follow tumor motions. Currently, there are no standard or best motion management options for all patients. However, motion reduction techniques may be simpler ways to address the motion issue while minimizing the injury to normal tissues. Current techniques to reduce the respiratory motion require either patient cooperation for breath-hold or abdominal compression, which may increase discomfort.

2.1.1 MRI-only Radiation Therapy Workflow

Several methods have been investigated in order to generate electron density maps from MRI for treatment planning, such as methods that manually identify tissue types and assign bulk densities[2-5], atlas-based methods to automate the process in generating electron density maps[6-9], and voxel-based methods to account for individual differences that are typically lacking in atlas-based methods[10-14]. These studies have shown promising results in terms of pseudo-CT quality, and demonstrated the potential of using MRI alone in the workflow for brain and prostate radiation therapy.

These encouraging results have prompted us to investigate the feasibility of using MRI-only in the abdominal radiotherapy workflow. The goals of using MRI in this workflow include: (1) the delineation of targets and organs-at-risk for treatment planning with enhanced distortion and intensity corrections, (2) the generation of pseudo-CT for dose calculations as well as the generation of digital reconstructed radiographs (DRRs) for image guidance using bony anatomy, and (3) target localization for treatment verification by matching treatment MRI (for MRI on rail) or pseudo-MRI (created from Cone-Beam CT (CBCT) for Linear Accelerator (LINAC) with kilo-voltage (kV) or mega-voltage (MV) on-board imager). To achieve the first goal, geometric distortions, intensity non-uniformity, and motion artifacts will need to be minimized to improve MR imaging quality for contouring and electron density mapping. To address the second goal, we will explore a probabilistic classification method to generate pseudo-CT and DRRs from MRI. This method accounts for individual differences and the mixing of tissue types within voxels that result in the generated pseudo-CT close to true individual anatomy. To address the third goal of using MRI for treatment guidance on the machines equipped with either MRI or kV- (or MV-) CBCT, we will explore the potential of synthesizing pseudo-MRI from CBCT to compensate for the limitation of CBCT in differentiating targets from normal tissues. Our proposed study incorporates MRI into treatment planning and image guidance workflow in order to improve the accuracy and ease of target delineation and localization for abdominal radiation therapy. The result will be not only useful in streamlining the radiation therapy workflow but could also be beneficial for attenuation corrections in PET-MRI.

2.1.2 Continuous Positive Airway Pressure (CPAP) for Motion Management

Continuous positive airway pressure (CPAP) has been used in patients with obstructive sleep apnea to maintain airway patency. Other indications include respiratory distress secondary to suspected congestive heart failure, acute cardiogenic pulmonary edema, pneumonia, and chronic obstructive pulmonary disease (asthma, bronchitis, emphysema) [15-17]. This technique provides a constant stream of pressurized air to the upper airways and lungs using a small air pump, tubing, and face/nose mask and may reduce diaphragm motion. An initial study using CPAP for lung radiotherapy indicates that CPAP significantly reduced lung tumor motion compared with free breathing, and therefore reduces treatment volume as well as lung dose. This study has shown the potential of CPAP as a new motion management option in radiotherapy with good reproducibility, simple implementation, and less needs in active patient cooperation [18].

Given these advantages of CPAP, we propose to incorporate CPAP into MRI-only abdominal radiation therapy workflow for motion reduction. The goals of using CPAP in this workflow are: (1) to reduce motion artifacts that degrade the quality of MR images, the quality of the electron density mapping, and the accuracy of target delineation, and (2) to improve targeting accuracy during radiation delivery and thus reduce the injury to neighboring normal tissues.

2.2 Hypotheses

Two primary hypotheses are considered in this study: (1) MRI-only abdominal radiation therapy will be a feasible workflow for treatment planning and target localization; (2) the use of CPAP will reduce tumor motion and change internal anatomy in a way that often protects critical organs, and thus allow precise radiation treatment for abdominal lesions while minimizing injury to neighboring normal tissues. We hypothesize that both technologies will be beneficial to patients with abdominal lesions.

2.3 Aims

Specific Aim 1: (1) Investigate methods to generate pseudo-CT to support radiotherapy treatment planning and image guidance for abdominal treatments. (2) Explore the feasibility to map CBCT to MRI intensities for improving the visualization of tumors and/or soft tissues for on-line treatment verification using CBCT-based methods. (3) Evaluate the potential role of 4D MRI and their associated pseudo-CT in target delineation for treatment planning and target localization for image guidance.

Specific Aim 2: Determine the effect of CPAP on pseudo-CT image quality, target delineation, tumor motion and dose to critical organs in abdominal radiotherapy.

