3. INCLUSION/EXCLUSION CRITERIA

3.1 Selection of Patient Subjects at the Albert Einstein College of Medicine/Montefiore Medical Center

To study the feasibility of a MRI-only workflow with/or without CPAP in abdominal radiation therapy, the following patients will be **included**:

- Eligibility Criteria
 - Patients have liver or pancreas tumors (either primary tumors or metastases) and are scheduled to be treated with radiotherapy (either 3D conformal or intensity-modulation radiotherapy (IMRT) with conventional or hypo-fractionation).
 - b. KPS ≥ 70
 - c. If a biopsy is performed, the patient is at least 1 week post-biopsy.
 - d. The patient's age must exceed 18 years.
 - e. The patients must be able to commit to T1-weighted, T2-weighted, Dixon fat and water, ultrashort-TE, and other clinical or research MR sequence images prior to treatment.
 - f. CPAP Eligibility: CPAP is a safe, effective form of therapy with rare complications. Relative contraindications include patients with bullous lung disease, fibrotic lung disease, Claustrophobia and recurrent sinus or ear infections. The absolute contraindications include obtundation /unconsciousness, chest wall trauma, suspected pneumothorax, persistent nausea/vomiting, active upper GI bleeding, history of recent gastric surgery, facial anomalies/trauma [15,16]. If there is any question about the above history and medical problems, the subject will be referred to a pulmonologist for consultation.
 - i. The patients with above contraindications are not CPAP eligible and are enrolled in Arm 1 for the protocol without CPAP
 - ii. The eligible patients are enrolled in Arm 2 for the protocol with CPAP.

Exclusion Criteria:

- Patients who meet the following criteria:
 - a. Any medical condition, which would make the imaging studies unsafe or poorly tolerated
 - b. Known allergic reaction to contrast or shellfish
 - c. Implanted metal devices or foreign bodies that serve as a contraindication to MR imaging
 - d. Creatinine > 1.4 mg/dl and Creatinine clearance < 20 mg/dl.
 - e. Uncontrolled, clinically significant cardiac arrhythmias
 - f. Severe claustrophobia
 - g. Pregnant female
 - h. KPS < 70

3.2 Selection of Healthy Volunteers at the Albert Einstein College of Medicine/Montefiore Medical Center

To optimize the MRI scanning protocols with and without CPAP volunteers that meet the following eligibility criteria will be **included**:

Eligibility Criteria

- a. KPS ≥ 70

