4. STUDY DESIGN AND METHODS

4.1 Recruitment of Subjects

Patients having either liver or pancreas cancer, who will be treated with radiation therapy will be invited to participate in the study during patient consult.

We will enroll up to five volunteers in the preliminary study to optimize the MR scanning protocols to be used in the patient study. We will place flyers to recruit healthy volunteers from Montefiore Medical Center or Albert Einstein College of Medicine. All eligible volunteers that can undergo CPAP and MRI scanning will be accepted into the volunteer study. No remuneration to volunteers will be offered and there are no potential benefits other than the Radiology read of the MRI for incidental findings. There are no risks to volunteers participating in the study related to radiation exposure because only MRI will be performed.

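### Aim 2 promises the effect of CPAP on pseudo-CT quality, but the protocol specifies no within-patient MRI pair and no analysis that could show it

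*Combined protocol and SAP*

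**What the plan says.** Section 2.3 states Aim 2 as: "Determine the effect of CPAP on pseudo-CT image quality, target delineation, tumor motion and dose to critical organs in abdominal radiotherapy". Pseudo-CT quality is named first. Section 2.1.2 gives a matching purpose for CPAP: "to reduce motion artifacts that degrade the quality of MR images, the quality of the electron density mapping, and the accuracy of target delineation".

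The arms are not randomised. The protocol summary says "Arm 1 is for patients that are either not eligible for CPAP or that are unable to tolerate CPAP", and section 3.1 says "The patients with above contraindications are not CPAP eligible and are enrolled in Arm 1". For Arm 2 the summary continues: "These patients will undergo breath-hold CT without CPAP, 4D-CT with and without CPAP and 4D-MRI with CPAP". Section 4.3.2 repeats this and gives Arm 1 breath-hold MRI and 4D-MRI, both without CPAP. It lists T1, T2, Dixon and ultra-short TE images in both arms and states no CPAP condition for them in Arm 2.

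For the evaluation of CPAP the summary says "to this end CT images with and without CPAP will be used". Section 4.3.7 compares excursion, ITV and dose between the two Arm 2 CT datasets, and section 5.2 sizes the motion comparison. Section 4.3.4, on pseudo-CT evaluation, contains no comparison by CPAP state.

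**The concern.** A CPAP effect on pseudo-CT quality needs three things: MRI without CPAP, MRI with CPAP, and a CT reference suited to each. The protocol sets out the pair for 4D-CT but not for patient MRI. What it does specify is 4D-MRI in opposite CPAP states in two groups that differ by design.

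Section 2.1.2 leads readers to expect a result on electron density mapping. If one is drawn from the two arms, a difference between patients who can and cannot use CPAP could be read as an effect of CPAP. The listed contraindications include bullous and fibrotic lung disease and claustrophobia, which could plausibly bear on breathing or on lying still in the scanner.

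A second problem lies in the reference. Section 2.2 expects CPAP to "change internal anatomy in a way that often protects critical organs". If pseudo-CT from with-CPAP MRI is judged against a without-CPAP CT, that change in anatomy would be counted as pseudo-CT error.

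**Working it through.** **1. The plan's own figure.** Section 5.2 assumes a mean reduction of 12%, an SD of 13%, n = 21 and a two-sided paired t-test at alpha 0.01.

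- Noncentrality = (12/13) × √21 = 4.230.
- Critical t on 20 df = 2.845.
- Power = 0.902, against the stated 90%.

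The figure reproduces. It covers within-patient motion only. No effect size, SD or sample size is given for pseudo-CT quality.

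**2. What is specified for each group** (sections 4.1, 4.3.1 and 4.3.2).

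| Group | 4D-MRI | T1, T2, Dixon, ultra-short TE | CT |
|---|---|---|---|
| Arm 1 | without CPAP | listed | breath-hold and 4D, without CPAP |
| Arm 2 (up to 21) | with CPAP | listed, CPAP state not given | breath-hold without CPAP; 4D in both states |
| Volunteers (up to 5) | not listed by name | both states | none |

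Section 4.1 notes that volunteers have no radiation exposure "because only MRI will be performed". They therefore offer no CT against which to judge a pseudo-CT.

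- Patients with a stated MRI pair: 0.
- Patients with a possible but unstated pair, if the Arm 2 sequences are in fact repeated: up to 21.
- Patients with a stated 4D-CT pair: up to 21.

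**3. Planned analyses.** The summary, 4.3.7 and 5.2 evaluate CPAP on CT. Section 4.3.4 compares pseudo-CT with CT, without reference to CPAP. None of them compares pseudo-CT quality by CPAP state, either within patients or between arms.

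**4. Reference CT.** Section 4.3.4 builds plans on standard CT and maps them onto pseudo-CT. Section 4.3.2 says treatment planning uses CT without CPAP motion management, while the Arm 2 4D-MRI is with CPAP. A with-CPAP 4D-CT exists for Arm 2, but 4.3.4 does not say whether it is used.

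**5. Illustration of the arm contrast.** The documents give no selection difference in pseudo-CT error, so d (in SDs) is an assumed range. Suppose CPAP has no effect and the arms are compared by a two-sided two-sample t-test at alpha 0.01. The noncentrality is d / √(1/n₁ + 1/n₂).

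| Assumed d | 21 vs 21 (df 40, critical t 2.704): noncentrality, chance of a false CPAP effect | 21 vs 10 (df 29, critical t 2.756): noncentrality, chance of a false CPAP effect |
|---|---|---|
| 0.25 | 0.810, 3.6% | 0.651, 2.6% |
| 0.5 | 1.620, 15% | 1.301, 8.9% |
| 0.8 | 2.592, 46% | 2.082, 27% |

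The nominal rate is 1%. The 21 versus 21 case is the maximum of 42 patients at 1:1. The 10 is an assumption: section 5.2 closes the study once Aim 1 has its number and does not settle whether Arm 2 patients count towards it.

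A within-patient comparison would not be exposed to this selection difference. With 21 pairs its 95% CI half-width would be t(0.975, 20)/√21 = 0.455 SD of the within-patient difference.

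**The case against.** The strongest reply is that the sequences most closely tied to pseudo-CT may already be paired. Section 4.3.2 describes the T1, T2, Dixon and ultra-short TE acquisitions and then says the MR images will be used to create pseudo-CT. Their CPAP state in Arm 2 is unlabelled, not ruled out. This stands. A reader might infer that only a confounded arm contrast is possible, but the text shows only that no pair is specified.

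Second, nobody has planned the arm contrast. This also stands. A reader might take the false-positive rates above as the trial's error rates. The documents do not support that: both the test and the selection differences are assumed, and the rates fall if Arm 1 has fewer than 21 patients.

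Third, the reference CT in 4.3.4 is ambiguous, not demonstrably wrong. Nothing says that with-CPAP pseudo-CT will be judged against a without-CPAP CT, so the point holds only conditionally.

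Fourth, even if the unlabelled sequences are paired, 4D-CT in both CPAP states is not automatically a valid reference. Those sequences are not listed as 4D, and the only breath-hold CT in Arm 2 is without CPAP. A mismatch in breathing state would also count as pseudo-CT error. The remedy has to allow for this.

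Finally, the study is exploratory on MRI-only planning and its powered comparisons do not involve this outcome. That limits the consequence but does not remove the mismatch between the aim and the design.

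**Conclusion.** The point holds in a limited form. Section 2.3 commits to determining a CPAP effect on pseudo-CT quality. The protocol specifies no with/without-CPAP MRI pair in any patient and no analysis of this outcome. The one 4D-MRI contrast it allows is between arms formed by CPAP eligibility and tolerance, and cannot be attributed to CPAP. This rests on the acquisition lists and needs no assumed figure.

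Confidence is high that no pair is specified. It does not extend to saying that none will exist.

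A reader might also infer that Aim 2 as a whole fails. It does not: excursion, ITV/PTV and planned organ dose are paired through the Arm 2 4D-CT, and the motion endpoint keeps its 90% power at n = 21. Motion artifacts as such can also be viewed in the volunteers' paired MRI. The gap concerns pseudo-CT quality. It should be corrected, because it limits what the trial can conclude and costs almost nothing to repair.

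**What to change.** 1. In 2.3, limit inference on the effect of CPAP to the paired Arm 2 4D-CT outcomes: tumor excursion, ITV/PTV and planned organ dose. State that pseudo-CT error is reported by arm, descriptively, and that no CPAP effect is inferred from it.
2. In 4.3.4, state that each pseudo-CT is compared with the same patient's CT in the same CPAP state and, where available, the same respiratory state. For the Arm 2 4D-MRI, this is the with-CPAP 4D-CT already acquired.
3. State the CPAP condition of the Arm 2 T1, T2, Dixon and ultra-short TE images in 4.3.2. Only if they are already acquired in both states, with CT matched on respiratory state, should the sub-aim stay as a within-patient comparison. Section 4.3.2 should then say so, and the quality metric should be named.

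The cost is wording in these sections, with no added scans. The downside is that one sub-aim becomes descriptive. Sample size and the powered motion endpoint do not change.

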3. INCLUSION/EXCLUSION CRITERIA

3.1 Selection of Patient Subjects at the Albert Einstein College of Medicine/Montefiore Medical Center

To study the feasibility of a MRI-only workflow with/or without CPAP in abdominal radiation therapy, the following patients will be **included**:

- Eligibility Criteria
 - Patients have liver or pancreas tumors (either primary tumors or metastases) and are scheduled to be treated with radiotherapy (either 3D conformal or intensity-modulation radiotherapy (IMRT) with conventional or hypo-fractionation).
 - b. KPS ≥ 70
 - c. If a biopsy is performed, the patient is at least 1 week post-biopsy.
 - d. The patient's age must exceed 18 years.
 - e. The patients must be able to commit to T1-weighted, T2-weighted, Dixon fat and water, ultrashort-TE, and other clinical or research MR sequence images prior to treatment.
 - f. CPAP Eligibility: CPAP is a safe, effective form of therapy with rare complications. Relative contraindications include patients with bullous lung disease, fibrotic lung disease, Claustrophobia and recurrent sinus or ear infections. The absolute contraindications include obtundation /unconsciousness, chest wall trauma, suspected pneumothorax, persistent nausea/vomiting, active upper GI bleeding, history of recent gastric surgery, facial anomalies/trauma [15,16]. If there is any question about the above history and medical problems, the subject will be referred to a pulmonologist for consultation.
 - i. The patients with above contraindications are not CPAP eligible and are enrolled in Arm 1 for the protocol without CPAP
 - ii. The eligible patients are enrolled in Arm 2 for the protocol with CPAP.

Exclusion Criteria:

- Patients who meet the following criteria:
 - a. Any medical condition, which would make the imaging studies unsafe or poorly tolerated
 - b. Known allergic reaction to contrast or shellfish
 - c. Implanted metal devices or foreign bodies that serve as a contraindication to MR imaging
 - d. Creatinine > 1.4 mg/dl and Creatinine clearance < 20 mg/dl.
 - e. Uncontrolled, clinically significant cardiac arrhythmias
 - f. Severe claustrophobia
 - g. Pregnant female
 - h. KPS < 70

3.2 Selection of Healthy Volunteers at the Albert Einstein College of Medicine/Montefiore Medical Center

To optimize the MRI scanning protocols with and without CPAP volunteers that meet the following eligibility criteria will be **included**:

Eligibility Criteria

- a. KPS ≥ 70
- b. The volunteers' age must exceed 18 years.
- c. The volunteers must be able to undergo T1-weighted, T2-weighted, Dixon fat and water, ultrashort-TE, and other clinical or research MR sequence images prior to treatment.

d. CPAP Eligibility: CPAP is a safe, effective form of therapy with rare complications. Relative contraindications include volunteers with bullous lung disease, fibrotic lung disease, Claustrophobia and recurrent sinus or ear infections. The absolute contraindications include obtundation /unconsciousness, chest wall trauma, suspected pneumothorax, persistent nausea/vomiting, active upper GI bleeding, history of recent gastric surgery, facial anomalies/trauma [15,16]. If there is any question about the above history and medical problems, the volunteer will be not be included in the pilot study.

Exclusion Criteria:

- Volunteers who meet the following criteria:
 - a. Any medical condition, which would make the imaging studies unsafe or poorly tolerated
 - b. Implanted metal devices or foreign bodies that serve as a contraindication to MR imaging
 - c. Uncontrolled, clinically significant cardiac arrhythmias
 - d. Severe claustrophobia
 - Pregnant female
 - f. KPS <70

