4.2 Registration Procedures

- Patients who agree to participate in the study and who provide written informed consent will be enrolled.
- Patients must meet all eligibility criteria listed in Section 3. The study coordinator will verify eligibility, assign a case number, and register the patient prior to study specific participation. The following information will be recorded:
 - Protocol number
 - Patient's initials
 - Patient's medical record number
 - Patient demographic data, including gender, birth date, and race.

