4.3 Study Design

4.3.1 A Volunteer Study to Optimize MRI Scanning Protocols with and without CPAP

Prior to enrolling patients in the study, a volunteer study will be conducted to optimize MRI scanning protocols with and without CPAP. The purpose of the volunteer study is to gain experience in using CPAP, to investigate appropriate MR imaging protocols with sufficient image resolution and contrast, and to test and streamline the workflow to minimize possible patient discomfort. Volunteers will not receive any MR contrast as part of their MR imaging and will be imaged two times once without the use of CPAP and once using CPAP employing the following

MR sequences: T1-weighted, T2-weighted, Dixon fat/water, ultra-short TE and other clinical or research MR sequences.

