4.3.2 Image Acquisitions: CT, MRI, CBCT and orthogonal kV/MV images

We are planning to enroll a maximum of 42 patients into this study. Prior to abdominal radiotherapy, all eligible participants will undergo both CT and MRI scans in the radiotherapy treatment position. Two scanning protocols (Arm 1 and Arm 2) will be performed according to their CPAP eligibility.

- (1) Arm 1: For patients not eligible for CPAP or unable to tolerate CPAP
 - Breath-hold CT and 4D-CT without CPAP
 - Breath-hold MRI and 4D-MRI without CPAP
 - T1-weighted, T2-weighted, Dixon fat/water, and ultra-short TE images
- (2) Arm 2: For patients eligible for CPAP and able to tolerate CPAP
 - Breath-hold CT without CPAP
 - 4D-CT with and without CPAP
 - 4D-MRI with CPAP
 - T1-weighted, T2-weighted, Dixon fat/water, and ultra-short TE images

CT scans will be performed in the axial scanning mode with ~2 mm slice thickness over the entire abdomen region for treatment planning and dose calculations.

MRI images using standard clinical imaging sequences will be acquired, including T1-weighted, T2-weighted, and Dixon fat and water images. Additional MRI scans, such as ultrashort-TE (UTE) images, will follow MRI safety guideline of FDA and will be optimized based on phantom and volunteer studies before clinical studies. Gadolinium-based contrast may be administered per institutional routine and research protocol. The MRI scanning sequences for these MRI images will be optimized to achieve optimal resolution (~ 2 mm) and contrast with minimized geometric distortion (< 2 mm). MR images will be used (1) to delineate the targets following the standard treatment planning process, and (2) to create pseudo-CT for dose calculations and to be compared with CT-based dose calculations.

Patients will receive standard radiotherapy to liver or pancreatic lesions using 3D-conformal or IMRT techniques (using CT-based planning without CPAP motion management). Prior to each treatment delivery, patients will undergo kV/MV orthogonal images and CBCT scans, and the CBCT scans will be compared with the planned CT to verify treatment position. In off-line, the CBCT scans and kV/MV orthogonal images will be compared with pseudo-CT and DRRs that are created from pseudo-CT.

4.3.3 CPAP Procedures for Eligible Patients Enrolled in Arm 2

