6 EXPECTED ADVERSE EVENTS

6.1 MRI Scans

MRI Scan:
Anxiety/Stress
Claustrophobia
Discomfort

Gadolinium:
Allergic reaction to contrast agent
Headache
Nausea
Vomiting
Rash
Temporary low blood pressure
Nephrogenic Systemic Fibrosis (NSF)/Nephrogenic Fibrosing Dermopathy (NFD).

NOTE: Precautions should be exercised for patients with a history of grand mal seizures, severely impaired renal function or hemolytic anemia. The very unlikely possibility of a reaction, including anaphylactic or cardiovascular reactions, should be considered especially for patients with a known sensitivity to Gadolinium or history of asthma. Nephrogenic Systemic Fibrosis (NSF) or Nephrogenic Fibrosing Dermopathy (NFD) (kidney disorders), may occur in patients with moderate to end-stage kidney disease after they have had a MRI scan with gadolinium-based contrast agent.

Needle Placement:
Minor discomfort;
Bleeding;
Infection;
Bruising.

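### Exclusion 3.1(d), the protocol's only numeric renal limit, gives clearance in a unit it cannot have and leaves unclear whether one limit or both exclude; no renal cut is stated for gadolinium

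*Combined protocol and SAP*

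**What the plan says.** Among the patient exclusions in Section 3.1, item (d) reads "Creatinine > 1.4 mg/dl and Creatinine clearance < 20 mg/dl". The list opens with "Patients who meet the following criteria". Item (b) of the same list is "Known allergic reaction to contrast or shellfish", and item (a) is a general provision: "Any medical condition, which would make the imaging studies unsafe or poorly tolerated". No other section gives a numeric renal limit, corrects the unit in (d), or says how its two conditions combine.

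Section 4.2 says who applies the list and when: "The study coordinator will verify eligibility, assign a case number, and register the patient prior to study specific participation".

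On contrast, Section 4.3.2 says "Gadolinium-based contrast may be administered per institutional routine and research protocol". Section 4.3.1 says "Volunteers will not receive any MR contrast as part of their MR imaging", so only patients can be exposed.

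Section 6.1 advises precaution, without a number, in patients whose renal function is severely impaired. It adds that nephrogenic systemic fibrosis (NSF) or its dermopathy form "may occur in patients with moderate to end-stage kidney disease after they have had a MRI scan with gadolinium-based contrast agent".

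**The concern.** There are two drafting faults in one line, and a gap beside it.

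- **Unit.** Clearance is a volume per unit time. A limit of 20 mg/dl cannot be applied to it.
- **Conjunction.** The 'and' can mean that both conditions must be met, or that the item lists two exclusions. The two meanings give opposite decisions for many patients with raised creatinine, and nothing tells the study coordinator which to use.
- **Contrast.** Section 6.1 places the NSF risk from moderate disease upward. The literal reading of (d) acts only below a clearance of 20, and 4.3.2 gives no renal condition of its own.

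Two things are at stake. Two members of staff could make different eligibility decisions on the same patient. Also, for patients with impaired kidneys who are given gadolinium, protection against a risk the protocol names would rest on clinical judgement and on a routine the protocol does not describe.

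**Working it through.** The plan has no figure to reproduce here. The check is of logic, followed by an illustration.

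**1. Logic.** Take clearance (CrCl) in mL/min and write Cr for serum creatinine in mg/dl.

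| Cr | CrCl | Joint reading (both needed) | Separate reading (either suffices) |
|---|---|---|---|
| 1.4 | 36 | not excluded | not excluded |
| 1.6 | 36 | not excluded | excluded |
| 1.4 | 19 | not excluded | excluded |
| 1.6 | 19 | excluded | excluded |
| 3.0 | 20 | not excluded | excluded |

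The readings differ whenever exactly one condition holds. On the joint reading, nobody with clearance of 20 or more is excluded by (d), whatever the creatinine. This needs no formula.

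**2. Illustration.** The documents give neither a clearance formula nor patient characteristics, so these are assumptions. Cockcroft-Gault is CrCl = k / Cr, with k = (140 − age) × weight / 72, multiplied by 0.85 for women. The grid is age 50 to 80 in steps of 5 (7 values), weight 50 to 90 kg in steps of 10 (5 values) and both sexes: 7 × 5 × 2 = 70 profiles.

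- Smallest k (woman, 80 years, 50 kg): 60 × 50 × 0.85 / 72 = 35.42.
- Largest k (man, 50 years, 90 kg): 90 × 90 / 72 = 112.5.

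**3. Does the 1.4 limit act on the joint reading?** Clearance falls below 20 once Cr exceeds k / 20. That is 35.42 / 20 = 1.77 for the smallest k and 112.5 / 20 = 5.6 for the largest. Every profile is therefore already above 1.4 when its clearance reaches 20, and the creatinine condition changes no decision on this grid.

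**4. How far apart are the readings at Cr 2.0?** Clearance runs from 35.42 / 2 = 17.7 to 112.5 / 2 = 56.25. Only two profiles fall below 20: a 50 kg woman of 80 (17.7) and one of 75 (65 × 50 × 0.85 / 72 / 2 = 19.2). So 68 of 70 remain eligible under (d) on the joint reading. On the separate reading 0 of 70 do, because 2.0 exceeds 1.4.

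**5. What passes on both readings?** Cr of exactly 1.4 is the highest creatinine that the separate reading admits. There, clearance runs from 35.42 / 1.4 = 25.3 to 112.5 / 1.4 = 80.4. The documents do not define moderate disease, so a range of assumed cuts is shown.

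| Cr | below 30 | below 45 | below 60 |
|---|---|---|---|
| 1.4 | 4 of 70 | 31 of 70 | 57 of 70 |
| 1.0 | 0 of 70 | 6 of 70 | 26 of 70 |

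These are counts of profiles on a uniform grid, not expected numbers of patients.

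**The case against.** The unit is a visible slip. A coordinator would almost certainly read it as mL/min, and that part alone would be editorial.

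The two readings are also not equally supported. Item (d) is one lettered entry joined by 'and', other exclusions have their own letters, and item (b) uses 'or' for alternatives. This makes the joint reading the literal one. It does not settle intent, because that reading leaves the 1.4 limit with almost nothing to do. The lead-in to the list gives some support, though weak, for treating the limits separately.

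Being eligible is not the same as receiving gadolinium. Contrast is optional, the sequences listed in 4.3.2 are not said to require it, and a protocol may rely on a local contrast policy without reproducing it. These points stand, and they limit who could be harmed.

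A reader might infer that patients with a clearance of about 36 are admitted on any reading and exposed to NSF risk. The documents do not support that. Such a patient (for example an 80-year-old man of 60 kg at Cr 1.4: 60 × 60 / 72 / 1.4 = 35.7) is only shown not to be excluded by (d). Exclusion 3.1(a), the precaution in 6.1, and the institutional routine and research protocol cited in 4.3.2 could each still protect him. The figure also depends on an assumed formula and matches no threshold in the text. Nor can it be said that the institutional routine is inadequate; it is simply not described.

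**Conclusion.** The concern holds as a faulty eligibility threshold with a bearing on patient safety, and it should be fixed. The wrong unit and the unresolved conjunction are plain in the text and are corrected nowhere. That the literal reading excludes nobody with clearance of 20 or more follows from logic alone, once mL/min is taken as the intended unit.

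The 68 versus 0 of 70 at creatinine 2.0 shows how far the readings can diverge. It rests on Cockcroft-Gault and on an assumed grid. How many of the maximum of 42 patients would be affected is unknown.

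The mismatch with the 6.1 risk group is a gap in what the protocol states. It does not show that patients at risk would be given contrast. The provisions that might prevent this carry no number, or are not described, so their effect cannot be confirmed from the documents. Healthy volunteers are outside the issue.

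**What to change.** **Section 3.1(d).** Write the clearance limit in mL/min and state explicitly whether either limit excludes or both must be met, as the sponsor intends. Simply replacing 'and' with 'or' would presume the stricter intent. It would exclude all 70 illustrative profiles at creatinine 2.0, with clearances up to about 56, and would not address patients with creatinine at or below 1.4 and reduced clearance.

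**Section 4.3.2.** This is the more important change. Add a sentence that gadolinium is withheld, with non-contrast MRI only, below a clearance or eGFR cut that covers the group named in 6.1. The clinical team should set the cut, or the sentence should name the institutional policy that does.

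**Cost.** One corrected line and one added sentence. Some patients would be scanned without contrast, which may reduce lesion visibility for them, and some would be excluded if either limit is meant to suffice. Endpoints, sample size and power do not change.
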